2.5. Definitions for primary endpoint

2.5.1. Determination of Treatment Success/Failure

Treatment success is defined as controlled ocular inflammation (see Table 2) in both eyes with 7.5 mg/day of prednisone, no periocular or intravitreal corticosteroid injections after the first 90 days of follow up, and ≤ 2 drops/day of topical 1% prednisolone acetate at the 6 month visit without treatment failure any point due to safety, tolerability or futility. Patients can stop medication at any time, but that in and of itself does not count as a treatment failure.

Table 2: Criteria for controlled inflammation

Parameter	Definition of control
Anterior chamber cells*	$\leq 0.5+$
Vitreous haze**	$\leq 0.5+$
Choroid & retina***	No active inflammation or retinal vasculitis posterior to the equator

*SUN criteria³⁰; ** NEI vitreous haze grading scale³¹ *** Cystoid macular edema is not sufficient to be called active inflammation

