2.5.2. Treatment failure

- Failure due to efficacy:** Patients can be declared a treatment failure due to futility and be declared a treatment failure and enter Phase II **at any time during follow-up** if the following occurs: The treating physician determines that it is futile to continue the current study medication due to persistent, uncontrolled inflammation that appears to be non-responsive to treatment. This option of declaring futility should only be declared if treatment with study medication seems completely unlikely to be able to control inflammation. Since the medications take up to a few months to fully take effect, increase in inflammation early on in the trial is not an indication of treatment failure. Corticosteroids may be increased in the case of increased inflammation.

Efficacy will be judged at the primary endpoint of 6 months. Specifically, at 6 months, if there is a lack of efficacy, patients will be declared a treatment failure and enter Phase II if the following occurs: The patient does not have controlled inflammation (see Table 2) with a prednisone dose of 7.5 mg/day and less than or equal to 2 prednisolone acetate 1% drops per day by 6 months.

- Failure due to intolerance:** Patients who experience severe symptoms thought to be related to the drug should try a dose reduction if they are willing. If this is not successful and the patient is unable to continue their

medication due to symptoms and is also not willing to continue, treatment failure can be declared. Please refer to Table 5 for dose reduction guidelines. Trial of a dose reduction is strongly encouraged, however it **is not required** for a patient to be determined a treatment failure due to intolerability.

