< 7.5 & ≥ 5	2 – 4	1 - 2.5
< 5 & ≥ 2.5	2 - 4	1.5 - 2.5
< 2.5 & ≥ 1	2 – 4	1
0		

NOTE: When beginning Phase I (6-12 months), hold patient at 7.5 mg/day, for at least one week.

Directions for Rescue Taper

Reactivations can be mild or severe. Mild reactivations are considered an increase in inflammation up to the 1+ level in anterior chamber cell or vitreous haze. Severe reactivations are considered an increase in inflammation up to the 2+ level or higher in anterior chamber cell or vitreous haze. Retinal/choroidal lesions may be considered mild or severe at the discretion of the study physician.

If uveitis reactivates:

- Increase oral prednisone up to a dose of 1 mg/kg for severe reactivations, or for mild reactivations, up to double the dose at which the flare occurred, until uveitis is controlled. Then re-taper according to the guidelines.

Uveitis is considered non-responsive if inflammation does not increase but does not further improve after the first 4 weeks of treatment on 1mg/kg oral prednisone.

If uveitis is non-responsive:

- Hold the current dose of prednisone for an additional week. If still no improvement, treatment failure due to futility may be declared, and patients may proceed to Phase II. Alternatively, other therapies may be added, but these should be noted as a protocol deviation.
- If treatment failure is declared due to futility in Phase I, before the primary endpoint of 6 months, patients may switch to Phase II. Patients who refuse to switch to Phase II should be encouraged to return for a 6-month visit. Patients who switch to Phase II will already be followed.
- If treatment failure is declared due to futility in Phase II, before the primary endpoint of 6 months, patients will be treated according to best medical judgment. If treatment failure is declared prior to 6 months, Phase I and Phase II, every attempt must be made to bring patients back for their 6 month assessment.

After suppression of uveitis is once again achieved (either in the case of reactivation or non-response) follow the taper guidelines for Phase I. Patients who have failed the treatment to which they are randomized will then switch treatments, begin Phase II, and follow the same taper guidelines as Phase I (0-6 months). If patients flare during Phase II, they can follow directions for the rescue taper listed above. Patients who fail the second treatment at the 6 month endpoint will be treated as per the investigators discretion.

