4.1.2. Phase II: Rescue treatment

In case of the first randomized treatment failure due to intolerability or lack of efficacy within the first six months of treatment, the treatment assignment will be switched to the alternate treatment. At this point, the patient will receive the antimetabolite not originally randomized to and will be followed an additional 6 months or until failure of the second treatment.

Patients will be given 2 weeks to enter into Phase II after treatment failure in Phase I. If patients do not enter within the 2-week window, they should be treated according to best medical judgment of their physician. If the physician believes a patient would benefit from treatment in Phase II, but there is an exceptional circumstance preventing the patient from entering Phase II within the 2-week window, contact the Coordinating Center for assistance.

Guidelines for Visit Schedule II

- Day 1 corresponds to the Baseline-II visit, which is also the first day the patient receives rescue treatment with the medication not initially received. Day 1 may be its own visit date (i.e. if within 2 weeks of the end of Phase I). Alternatively Day 1 may be the same day as the last day of Phase I. All study forms should indicate what visit it is for Phase I and what visit it is for Phase II, if applicable. See the following example below.

Phase	 1	 2								
Visit	 Baseline	 Two weeks	 Non-study visit (treatment failure only)							
Month:	 1	 2	 3	 4	 5	 6	 9	 12		

- Visit dates are determined based on the date of the Baseline-II visit (which may be the same date as Phase I treatment failure), and may not be changed.
- The Baseline-II visit form should be completed to gather information on any changes in health status or medications.
- There should be a minimum of 2 weeks between each study visit.
- Data for the follow-up visits may be collected anytime within the visit window.

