2.3 Specific Aims

2.3.1 Specific Aim 1

Primary Objective. The primary objective of the study is **to establish which immunosuppressive treatment, methotrexate or mycophenolate mofetil, results in a higher rate of corticosteroid-sparing treatment success, on an intent to treat basis.** Specifically, we will compare the fraction of subjects who achieve treatment success at six months (as defined in the Manual of Operations Section 2.5.1) between the two groups.

Primary Outcome. The primary outcome for Specific Aim 1 will be the difference in the proportion of patients assigned to mycophenolate mofetil vs. methotrexate who achieve treatment success (as defined in the Manual of Operations Section 2.5.1).

Patients who experience success at 6 months with the drug to which they were originally randomized (in Specific Aim 1) will continue on the same drug for an additional 6 months. This will be called Phase I (6-12 months). Patients will then be seen every 3 months (and will be examined at 9 months and at 12 months), until success at 12 months or treatment failure at any time. Patients who fail treatment before 12 months with the initial drug will be removed from the study and treated according to best medical judgment.

Secondary Objectives

- To determine whether patients exhibit a difference in time to control of inflammation within the first six months.
- To determine whether patients exhibit a difference in time to corticosteroid sparing control of inflammation within the first six months.
- To evaluate the proportion of patients achieving treatment success at 5 months and sustaining, for at least 28 days, to 6 months.
- To evaluate a difference in control of inflammation in the posterior/pan anatomic locations only, assessed at by six months.
- To evaluate a difference in control of inflammation in the interior and anterior/intermediate anatomic locations only, assessed at by six months.
- To determine whether there is a change in best spectacle-corrected visual acuity at six months.
- To determine whether patients treated exhibit a difference in health related quality of life at six months.
- To determine if there are differences in discontinuing treatment due to each of the following reasons: safety, intolerability or lack of efficacy at six months.
- To determine whether patients exhibit a difference in the proportion of patients having macular edema at 6 months
- To determine whether patients exhibit a difference in macular thickness at 6 months

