Patients who experience treatment failure (as defined in the Manual of Operations) with the drug to which they were originally randomized in Specific Aim 1 will discontinue the current treatment and be administered rescue therapy with the second drug (in a masked fashion). This will be called Phase II. Treatment failure with the first drug is defined as the inability to continue taking the drug to which the patient has been randomized, either due to intolerability, safety concerns, or lack of efficacy.

Upon declaration of treatment failure, the patient will be automatically screened for Aim 2. If eligibility criteria are met, the second treatment will be administered and data will be collected for the Phase II baseline visit. Patients will then be seen every 4 weeks until 6 months or until treatment failure with the second drug. Treatment failure and success will be defined as in Aim 1. Patients who fail treatment before 6 months with the second drug will be removed from the study and treated according to best medical judgement.

Primary Outcome. The primary outcome is the fraction achieving treatment success at 6 months after starting Phase II. Treatment success is defined as in Aim 1 and described in the Manual of Operations Section 2.5.1.

Secondary Objectives. All of the secondary 6 month objectives listed for Aim 1 will be examined for Aim 2.

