- Baseline best spectacle-corrected visual acuity, vitreous haze, macular thickness
- Vasculitis

Inclusion of Data

- Data will be included for all outcomes within the window period of -2 weeks to +4 weeks around the 6 Month Visit date for Phase I (0-6 months).
- Data will be included for all outcomes within the window period of -2 weeks to +4 weeks around the 12 Month Visit date for Phase I (6-12 months).
- Data will be included for all outcomes within the window period of -2 weeks to +4 weeks around the 6 Month Visit for Phase II (0-6 months).

3.2.2 Specific Aim 1

Primary Analysis.

The primary analysis will be a logistic regression model, predicting treatment success at 6 months based on treatment arm. We wish to aggregate sites within countries, and countries within treatments provided we find no evidence of heterogeneity of sites or countries.

Specifically, the pre-specified primary analysis will be performed as follows. We denote the assignment group of patient i , $i=1, \dots, N$ (where N is the number of subjects) by X_p^1 which equals 0 when the patient is in the methotrexate group and 1 when the patient is in the mycophenolate mofetil group. The outcome variable is Y_p which is 1 if treatment success of patient i is achieved by six months, and 0 otherwise. The variable is missing if the patient is lost to follow-up or drops out of the study for reasons other than discontinuation due to intolerance or adverse events; if the patient discontinues the medication due to intolerance or adverse events such as abnormal laboratory findings, the value is 0.

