3.5 Missing data and loss to follow-up

Values of the primary study endpoint (treatment success at six months) cannot be analyzed when the individual is lost to follow-up. We distinguish information which is missing because of possible progression of the underlying condition we wish to treat from information which is lost for some other reason. Earlier, we discussed methods for handling missing values for specific

uveitis fields in individuals. The discussion in this section applies only to loss to follow-up or to dropping out of the study. As emphasized in Carpenter & Kenward (2007), “there can be no universal analysis when data are missing”. Our purpose is to vary the assumptions as well as the methods, to establish that the estimates of the treatment effect are robust as such assumptions are varied.

Our priority is the preservation of the intent to treat principle. We propose to report the results from all of the following methods:

1. The use of regression-based multiple imputation, based on all observed data for the patient.
2. Use of longitudinal generalized linear mixed effects regression, with visit as a covariate, and including a random effect for each person and for each eye within each person, using all the available measurements on each individual
3. Sensitivity analysis in which missing final outcome values are assigned success or failure, and the analysis conducted conditional on these assignments.
4. Analysis of complete cases only (individuals for which the six month follow-up is available)

However, we are proposing that **method 4 (complete case analysis) be considered the primary outcome**, based on recommendation by the DSMB. All other analyses are to be considered supplementary.

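### The SAP's missing-data rule for the primary outcome drops patients declared futility failures who never return at month 6, although the adopted success definition makes them known failures

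*Combined protocol and SAP*

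**What the plan says.** SAP 2.3.1 compares the fractions of subjects who "achieve treatment success at six months (as defined in the Manual of Operations Section 2.5.1"). That protocol section requires control at month 6 "without treatment failure any point due to safety, tolerability or futility". Protocol 2.5.2 lets futility be declared at any time in follow-up: "Patients can be declared a treatment failure due to futility and be declared a treatment failure and enter Phase II". SAP 2.3.2 gives the grounds for first-drug failure as "either due to intolerability, safety concerns, or lack of efficacy".

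SAP 3.2.2 (Specific Aim 1, Primary Analysis) first codes the outcome Y as 1 for success and 0 in all other cases. The next sentence makes Y missing when the patient is "lost to follow-up or drops out of the study for reasons other than discontinuation due to intolerance or adverse events", and gives an explicit 0 only for discontinuation on those two grounds. SAP 3.5 then names method 4 as primary: "Analysis of complete cases only (individuals for which the six month follow-up is available"). The other methods are supplementary.

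The protocol shows how a futility failure can end up without a month-6 visit. On refusers, section 3.2.1 says: "Patients who refuse to switch to Phase II should be encouraged to return for a 6-month visit". On late entrants, section 4.1.2 says: "If patients do not enter within the 2-week window, they should be treated according to best medical judgment of their physician".

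**The concern.** The protocol recognises three grounds for failure before month 6: safety, intolerance and futility. The SAP's missing-data rule protects two of them. A patient declared a futility failure who then leaves has a known outcome under the definition the SAP adopts, yet the SAP's own rules make that outcome missing and remove the patient from the primary analysis.

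All the patients removed are failures, so each removal raises the observed success rate in that arm. If the two arms lose different shares of their failures, the primary treatment comparison moves, and it can move either way. Two analysts could also compute different primary outcomes from the same data, depending on which section they followed.

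There is a second, weaker point. Read literally, the parenthesis in SAP 3.5 would also exclude intolerance and safety failures with no month-6 visit, whom SAP 3.2.2 codes 0.

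**Working it through.** **Inputs from the SAP.** Section 3.4.1: success 0.40 on methotrexate and 0.60 on mycophenolate mofetil, 108 per arm, 10% loss by six months, two-sided alpha 0.05, 80% power. Section 3.4.2: discontinuation for tolerability plus safety of 13% + 5% = 18% on methotrexate and 4% + 5% = 9% on mycophenolate.

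**The plan's own figure.** Formula (5) gives 2N = 4 × (1.96 + 0.8416)² × 0.25 / 0.20² = 196.2, or 98.1 per arm; dividing by 0.9 gives 109.0, close to the stated 108. With 108 × 0.9 = 97.2 analysed per arm, the same approximation gives power Φ(0.20 / √(2 × 0.25 / 97.2) − 1.96) = 79.6%. The sample size is not in question.

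**Effect of dropping known failures.** Let g be the share of an arm's failures that is dropped. The documents do not give g, so every value below is an assumption.

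- Observed success rate = p / (p + (1 − p)(1 − g)).
- Observed odds ratio = 2.25 × (1 − g for methotrexate) / (1 − g for mycophenolate), where 2.25 = (0.6/0.4) / (0.4/0.6).
- Expected failures: 108 × 0.60 = 64.8 and 108 × 0.40 = 43.2.
- Planned loss is 10.8 per arm, so g cannot exceed 10.8/64.8 = 16.7% or 10.8/43.2 = 25%.

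| g, methotrexate / mycophenolate | Patients dropped | Observed rates | Difference | Odds ratio |
|---|---|---|---|---|
| 5% / 5% | 3.2 / 2.2 | 41.2% / 61.2% | 20.0 points | 2.25 |
| 10% / 10% | 6.5 / 4.3 | 42.6% / 62.5% | 19.95 points | 2.25 |
| 10% / 5% | 6.5 / 2.2 | 42.6% / 61.2% | 18.7 points | 2.13 |
| 5% / 10% | 3.2 / 4.3 | 41.2% / 62.5% | 21.3 points | 2.38 |

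**Power.** The approximation is the same. Total loss is held at 10% including the dropped failures, and the remaining loss is assumed unrelated to outcome, so 97.2 per arm are analysed. Power is 74% for 10%/5% and 84% for 5%/10%. If the dropped patients are returned as failures, the numbers analysed become 97.2 + 6.5 = 103.7 and 97.2 + 2.2 = 99.4 in the first case, and 100.4 and 101.5 in the second. Power is then about 81% in both.

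**No true difference.** With both drugs at 50% and 10%/5% dropped, the rates are 0.5/0.95 = 52.6% and 0.5/0.975 = 51.3%, a spurious 1.3 points. As an outer stress test, take 97.2 per arm and drop failures from one arm only. Dropping 5 gives 48.6/92.2 = 52.7%, a bias of 2.7 points, and rejection rises from 5% to about 6.6%. Dropping 10 gives 48.6/87.2 = 55.7%, a bias of 5.7 points, and rejection of about 12.2%. The last case puts nearly an arm's whole planned loss into this group and none of the other arm's, so it is a limit and not a forecast.

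**Literal reading of SAP 3.5.** Suppose a quarter of tolerability and safety discontinuations have no month-6 visit (assumed): 4.5% and 2.25% of the arms. Then g = 0.045/0.60 = 7.5% and 0.0225/0.40 = 5.6%. The rates are 41.9% and 61.4%, a difference of 19.5 points, and the odds ratio is 2.21.

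**The case against.** The best defence is that the intended coding is 0. SAP 3.2.2 first assigns 0 to everyone who is not a success, and SAP 2.3.1 points to a definition under which futility rules out success. Several SAP outcomes are taken at failure or at six months, which suggests that a declared failure has already reached its endpoint. Protocol 2.5.3 also says that missing visits does not make a patient a dropout. This shows likely intent but does not settle the text. The sentence after the general rule is more specific and overrides it for patients lost or dropping out. For those who simply do not come back, SAP 3.5 still asks for six-month follow-up.

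On the literal reading of 3.5, the objection is stronger. That section limits itself to loss to follow-up and dropout, and 3.2.2 expressly codes intolerance and adverse-event discontinuations 0. The parenthesis may be shorthand, so this remains a secondary point.

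On size, much of the objection stands. Most efficacy failures are judged at month 6 and have that visit, switchers stay in follow-up, and the protocol asks sites to seek month-6 data from the rest. Taking out the expected tolerability and safety failures (19.4 and 9.7) leaves about 45 methotrexate and 33 mycophenolate efficacy failures. The 6.5 patients in the 10% scenario are then about 14% of the methotrexate efficacy failures and 60% of that arm's planned loss. Nothing in the documents supports a twofold imbalance between arms.

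The imputation and assigned-outcome analyses (SAP 3.5), the lost-to-follow-up analysis (SAP 3.3.1) and the SAP's own caution about complete cases could reveal dependence on these patients. They are supplementary, however, and treat a recorded outcome as unknown.

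**Conclusion.** The concern holds. SAP 3.2.2 and 3.5 together exclude a patient whom protocol 2.5.1, adopted by SAP 2.3.1, makes a failure: one declared futile before month 6 who does not enter Phase II and does not return. The rule as written gives the wrong result for that patient, so this is more than a missing detail.

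The conclusion rests on the text. Its size rests on assumed shares. Equal shares leave the odds ratio at 2.25; a 10%/5% split in either direction moves it to 2.13 or 2.38 and power to 74% or 84%. The number of patients is probably small, and neither the frequency nor the direction can be read from the documents. It should be fixed because it affects the primary outcome and the correction is cheap.

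**What to change.** In SAP 3.2.2 and 3.5, state that:

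- Y = 0 for any treatment failure under protocol 2.5 occurring by month 6 (efficacy or futility, intolerance, safety, or a death the Medical Monitor judges drug-related), whether or not a month-6 visit exists.
- Y is missing only when no such failure occurred and there is no month-6 assessment.
- A complete case is a patient whose Y is known under these two rules.

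Two small edits belong with this. Tie discontinuation in 3.2.2 to a declared treatment failure, because protocol 2.5.1 says that stopping medication is not in itself a failure. Correct the SAP 3.2.1 reference from protocol section 2.6 to 2.5.1.

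No new data are needed: declared failures are on the Treatment Assessment Form, and drug-related deaths come from the Medical Monitor's determination. Observed success rates may be slightly lower. The SAP is subject to monitoring committee approval and complete cases were made primary on that committee's recommendation, so the change should go through it. The same coding should apply at the interim analyses, which use the same primary outcome and model.

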- Failure due to safety:** Patients who experience abnormal lab results meeting the designated threshold of a *non-serious adverse event* (e.g. AST or ALT increasing to twice the upper limit of normal) will immediately stop taking their medication. As these abnormalities are often reversible, patients whose abnormalities are classified as non-serious adverse events (see Table 3) will be *allowed 28 days to regain eligibility*. It is recommended that these patients repeat lab tests within 1-2 weeks of the initial abnormal result to see if the results return below the designated threshold (e.g. AST or ALT less than twice the upper limit of normal). If the lab results return below the designated threshold of a *non-serious adverse event* within 28 days, patients may be re-administered the study drug per protocol or at one of the designated dose reduction levels, at the investigator's discretion.

If lab results remain at or above the threshold of a *non-serious adverse event* for 28 days, this is classified as a serious adverse event and treatment failure will immediately be declared. At this point, patients will be treated according to the best medical judgment of their clinician and not switch to Phase II (if currently in Phase I). However, month 6 visit data and imaging should still be collected (Phase I and Phase II), if the serious adverse event occurs before the six month visit. For other non-serious adverse events (such as an opportunistic infection) the study drug may be stopped temporarily as per the discretion of the investigator. If an infection does not resolve within 28 days, it is considered a serious adverse event.

Table 3: Thresholds for classifying non-serious and serious lab abnormalities

	Non-Serious Adverse Event*	Serious Adverse Event
Leukocytes	>1,000 to <2,500/ μ L	\leq 1,000/ μ L
Platelets	20,000 to 75,000/ μ L	< 20,000/ μ L
Hemoglobin	\geq 6.5 to < 9 g/dL	< 6.5 g/dL
SGOT (AST) or SGPT (ALT)	2 to <5 times the upper limit of normal of the reference range	\geq 5 times the upper limit of normal of the reference range
Creatinine	\geq 1.5 to < 2 mg/dL	\geq 2 mg/dL

*NOTE: If any non-serious lab abnormality does not resolve within 28 days, then it must be classified as a serious adverse event, and treatment failure due to safety will be declared.

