For all non-laboratory SAEs, treatment failure cannot be declared until the Medical Monitor judges that the SAE is related to the study drug. This will require the investigator notifying the Medical Monitor about the event, and the Medical Monitor contacting the investigator regarding his determination. The Medical Monitor will determine two things: 1, whether this is a true treatment failure because the SAE is likely to be related to the study drug, and 2, whether it is safe to switch the patient to Phase II. If it is not safe to switch, the patient will be treated according to best medical judgment, and still be followed up at their 6 month visit (Phase I and Phase II).

If the investigator thinks the SAE is related to the study drug, he/she can stop the study medication anytime (including prior to determination of treatment failure by the Medical Monitor). If the investigator thinks treatment failure is likely (prior to hearing from the Medical Monitor) they should obtain all study assessments which would be collected at a treatment failure visit. However, the investigator will wait to complete the Treatment Assessment Form and officially declare treatment failure until they are instructed to do so by the Medical Monitor.

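### Read literally, SAP 3.2.2 scores any stop for intolerance or an adverse event as primary failure, while the MOP definition it adopts requires a declared failure; a small group controlled at month 6 gets opposite scores

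*Combined protocol and SAP*

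**What the plan says.** SAP 2.3.1 defines the primary outcome as the difference between arms in the proportion of patients "who achieve treatment success (as defined in the Manual of Operations Section 2.5.1". MOP 2.5.1 requires controlled inflammation in both eyes at the month-6 visit within the steroid limits, "without treatment failure any point due to safety, tolerability or futility". It adds that a patient may stop medication at any time and that stopping alone is not failure.

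MOP 2.5.2 sets out when a stop becomes a failure:

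- **Intolerance.** "Patients who experience severe symptoms thought to be related to the drug should try a dose reduction if they are willing"; if that does not work and the patient can neither tolerate nor accept the drug, failure can be declared. A dose reduction is encouraged but not required first.
- **Laboratory values at the non-serious threshold.** The drug stops at once. If values recover within 28 days, "patients may be re-administered the study drug per protocol or at one of the designated dose reduction levels", at the investigator's discretion. Failure follows only if the abnormality lasts 28 days. Laboratory values at the SAE threshold are failure immediately (MOP 5.6).
- **Other non-serious events.** "the study drug may be stopped temporarily as per the discretion of the investigator".
- **Non-laboratory SAEs.** "For all non-laboratory SAEs, treatment failure cannot be declared until the Medical Monitor judges that the SAE is related to the study drug". An investigator who suspects the drug "he/she can stop the study medication anytime (including prior to determination of treatment failure by the Medical Monitor").

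SAP 3.2.2 sets Y to 1 for success by six months and 0 otherwise. It makes Y missing for loss to follow-up or for dropout unrelated to intolerance or adverse events. It then adds, after a semicolon: "if the patient discontinues the medication due to intolerance or adverse events such as abnormal laboratory findings, the value is 0".

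**The concern.** The last clause of SAP 3.2.2 turns on why the medication was stopped. The definition it is meant to implement turns on whether failure was declared. The SAP's own example, abnormal laboratory findings, is a case where MOP 2.5.2 forces a stop that may never become a failure.

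For a patient who stopped for such a reason, had no declared failure and is controlled at month 6, the primary value is 1 under one text and 0 under the other. The analyst has to choose, and nothing prevents that choice from being made after unmasking. The non-inferiority analysis in SAP 3.2.2 (item 16) also rests on treatment success at 6 months.

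**Working it through.** **1. Compare the two rules, for a patient controlled at month 6 on the allowed steroid dose.**

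| Reason for stop | MOP 2.5.1–2.5.2 | SAP 3.2.2, literal |
|---|---|---|
| Intolerance, failure declared | 0 | 0 |
| Laboratory abnormality lasting 28 days, or at SAE level | 0 | 0 |
| Non-laboratory SAE ruled drug-related | 0 | 0 |
| Laboratory values recovered within 28 days, drug not restarted | 1 | 0 |
| Drug stopped for a non-laboratory SAE, later ruled unrelated, not restarted | 1 | 0 |
| Temporary hold, drug restarted | 1 | 0 only if a hold counts as discontinuing |

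The month-6 data for the last three rows should exist. MOP 2.5.3 says that neither a non-serious adverse event nor stopping study medication makes a patient a dropout. MOP 4.4.3 requires all forms whether or not the patient is taking drug.

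**2. Reproduce the planned sample size (SAP 3.4.1).** Inputs are 40% and 60% success, two-sided alpha 0.05, 80% power and 10% loss. Equation (5) gives 2N = 4 × (1.960 + 0.842)² × 0.25 / 0.04 = 196.2 before loss. The standard two-proportion formula gives 97 per arm, and 97/0.9 rounds up to 108, or 216 in total. With 97 evaluable per arm, power is 80.0%. None of this is disputed.

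**3. Size the disagreement.** SAP 3.4.2 (item 5) expects 5% safety discontinuations in each arm: 0.05 × 97 = 4.85 patients. The rules agree on most of these, so it is a rough ceiling for the safety groups. Let f be the share falling in the disputed rows. No document gives f; 10% to 50% is an assumption. Taking 40% (methotrexate) and 60% (mycophenolate) as controlled at month 6, the literal SAP coding removes 4.85 × f × 0.40 and 4.85 × f × 0.60 successes.

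| f | Successes lost, methotrexate / mycophenolate | Both arms: difference, power | Mycophenolate arm only: difference, power |
|---|---|---|---|
| 10% | 0.19 / 0.29 | 19.90 points, 79.6% | 19.70 points, 78.8% |
| 25% | 0.49 / 0.73 | 19.75 points, 79.0% | 19.25 points, 76.9% |
| 50% | 0.97 / 1.46 | 19.50 points, 78.0% | 18.50 points, 73.5% |

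If only the methotrexate arm were affected, the difference would rise to between 20.2 and 21.0 points. Power uses the pooled-variance two-proportion formula with no interim adjustment.

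**4. A wider bound.** MOP 2.5.2 only permits a declaration for intolerance, so some intolerance stops might also go undeclared. SAP 3.4.2 expects tolerability plus safety stops of 13% + 5% = 18% on methotrexate and 4% + 5% = 9% on mycophenolate. That is 17.5 + 8.7, or about 26 of the retained patients. If 10% to 25% were undeclared and 40% to 60% of those controlled in each arm (assumptions), about 1 to 4 patients would be scored differently. Taking 40% and 60% as the rates under the literal coding, MOP scoring would narrow the difference by about 0.4 to 1.3 points and power would be 78.6% to 74.3%.

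**5. Near the margin.** Read the non-inferiority rule as requiring the lower 95% limit of methotrexate minus mycophenolate to exceed −10 points. This is my reading, since the printed rule gives no sign. With 52/97 against 48/97, the Wald limit is −9.9. Rescoring one methotrexate patient (51/97) gives −11.0. The table was chosen to sit at the margin; it shows that one patient can matter, not that one is likely to.

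**The case against.** **The clause only sorts leavers.** It completes a sentence about when Y is missing, so it may mean just that patients who leave because of adverse events are 0 and not missing. A patient seen at month 6 would then be scored by the MOP, with no conflict. This reading is possible. But the clause speaks of discontinuing medication, not of leaving the study, and MOP 2.5.3 separates the two. The wording does not settle it.

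**Discontinuation is failure elsewhere in the SAP.** SAP 2.3.2 describes first-drug failure as being unable to continue for intolerability, safety or lack of efficacy, and SAP 3.2.2 (item 6) sorts discontinuations by the same reasons. That covers most permanent stops. It does not cover a patient whose laboratory values recovered but whom the investigator chooses not to restart, or one whose SAE was ruled unrelated.

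**The disputed groups are narrow.** This stands in part. A recovered patient who personally declines to restart may be merely non-compliant under MOP 2.5.3, and so arguably scored from month 6 under both texts. Temporary holds drop out if discontinuation means permanent discontinuation. SAP 4.2 adds that qualifier; SAP 3.2.2 does not.

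**Single-patient influence is already handled.** SAP 3.3.3 promises jackknife statistics. These delete observations and do not recode them. They would flag a fragile result without saying which code is right.

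**A stronger reading that fails.** A reader might infer that one rescored patient would overturn a superiority finding. For 41/97 against 55/97, an uncorrected chi-square gives p = 0.044, rising to 0.062 at 54/97. But SAP 3.2.2 plans a permutation P-value based on the blocked randomization, and Fisher's exact test on the first table already gives 0.062. That example does not show a flip under the planned test.

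**Conclusion.** Wrong as written, with a small expected effect. Taken literally, the SAP 3.2.2 clause contradicts the endpoint definition that SAP 2.3.1 adopts, and no other section resolves it. It would be too strong to say that the plan misclassifies intolerance and adverse-event stops in general, because the two rules agree on most of them. The disagreement is confined to patients controlled at month 6 with no declared failure, and the documents give no count.

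If both arms are affected alike, the cost is 0.1 to 0.5 points of treatment difference and at most 2 points of power. The lower power figures need the cases to fall all in one arm, or undeclared intolerance stops to be included. All these figures rest on assumed shares with no source in the documents. The practical consequence is an avoidable choice of primary coding that could matter only for a near-borderline superiority or non-inferiority result.

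**What to change.** Replace the clause in SAP 3.2.2 with:

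> *Y = 0 if treatment failure for safety, intolerance or efficacy/futility was declared under MOP 2.5.2. A stop for intolerance or an adverse event without a declared failure is scored from the month-6 assessment if there is one within the window, and is 0 if there is none for any reason, whether or not the patient is formally a dropout.*

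The last limb matters. Complete-case analysis is primary (SAP 3.5), and MOP 2.5.3 does not class a patient who merely misses visits as a dropout. A rule confined to patients who leave the study would let such adverse-event stoppers become missing.

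Report the literal SAP coding as a sensitivity analysis, with the number of patients scored differently in each arm. Settle the wording before unmasked analysis.

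The cost is one SAP sentence and one sensitivity run. No new data are needed, only a check of recorded stops against the Treatment Assessment Forms already collected.
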